Describe the procedures required for this study

Participants: Over 2 years we will recruit 18 (9 men and 9 women; to obtain 14 completers) non-treatment seeking cannabis smokers (21-45 years of age) who are also diagnosed with DSM-V criteria for **at least subthreshold** PTSD. Volunteers will undergo extensive medical and psychological screening to ensure eligibility.

Design: This is a double-blind, placebo controlled, within-subject study. Participants will be trained in study procedures and complete four, 8- hour outpatient laboratory sessions, with at least 72-hours between sessions for medication clearance (Table 1). As per our usual procedures, we will track the menstrual cycle and collect blood samples for estradiol and progesterone to verify menstrual cycle phase for a exploratory analysis. Blood will be drawn before baseline measurements of each session for both men and women. Blood from men will not be analyzed. We will also test for pregnancy every session with urine tests.

Drugs: Nabilone capsules (4 mg) will be obtained from Meda Pharmaceuticals, Inc., propranolol capsules (40 mg) will be obtained from Teva Pharmaceuticals, and cannabis cigarettes (0.0 and 5.6% .THC) will be provided by NIDA. Nabilone pills (4) and propranolol capsules (1) will be over-encapsulated in size 00 capsules using white, opaque lactose filler. For the placebo condition, 4 size 00 capsules containing lactose filler for nabilone and 1 size 00 capsule containing lactose filler for propranolol will be administered. The active (5.6% THC) and inactive (0.0% THC) cannabis cigarettes will also be visually identical. Drug administration will be randomized, double-blind, and double dummy.

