Visual Cue Task. The International Affective Picture System (IAPS) includes 1,000 images that vary in affective valence (pleasant versus unpleasant) and arousal (Lang et al., 1997). For this, participants are presented with images varying in valence (pleasant, neutral, and unpleasant), with pleasant and unpleasant stimuli matched for arousal levels. Images are presented for 6 sec followed by a 15 sec interval during which time the participant will rate his/her personal reaction to the image according to affective dimensions of valence and arousal using self-report scales (Bradley & Lang, 1994). During each session, 40 images will be presented: 10 pleasant, 10 neutral, 10 negative, 10 participant-specific trauma-related. The participant-specific trauma-related images will include images representing images that depict the type of trauma a specific participant has experienced (depicting violence, death, bodily injury, natural disasters, combat, and sexual assault). Presentation of images will be randomized and they will not be repeated across sessions.

Physiological Measures: *Skin Conductance (SC)* is an index of physiological arousal and a sympathetic nervous system response that is hypothesized to be dysregulated in PTSD (Pole, 2007) and has been shown to be a marker of reactivity to trauma-related cues in PTSD patients (Felmingham et al., 2011). SC to trauma related cues during the EST and the IAPS procedure will be measured using the BIOPIC Systems equipment and software that [name] has used for other studies. Under placebo conditions, trauma-related words on the EST and images are expected to elicit increases in SC; women will exhibit a more pronounced SC response to these cues. Active nabilone, cannabis, and propranolol are expected to dampen SC in response to trauma-related words and images.

Heart Rate and Blood Pressure. Heart rate will be continuously recorded using a heart rate

monitor (Polar FT60) starting 30 min before capsule administration and throughout the session. Both seated and standing blood pressure (Sentry II automated vital signs monitor; NBS Medical Services, Costa Mesa, CA) will be periodically monitored before capsule administration and until the end of the session.

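### The picture task shows new images in every session without saying that the four sets are equated or how they are paired with drug conditions, which adds avoidable noise to the drug-placebo contrasts

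*Protocol*

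**What the plan says.** All the relevant text is in the protocol, under the procedures required for the study.

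- **Design:** "This is a double-blind, placebo controlled, within-subject study". Participants "complete four, 8- hour outpatient laboratory sessions". "Drug administration will be randomized, double-blind, and double dummy". I read this as one drug condition per session: placebo and three active conditions.
- **Visual Cue Task, content:** "During each session, 40 images will be presented: 10 pleasant, 10 neutral, 10 negative, 10 participant-specific trauma-related". The trauma category consists of "images that depict the type of trauma a specific participant has experienced".
- **Visual Cue Task, allocation:** "Presentation of images will be randomized and they will not be repeated across sessions".
- **Visual Cue Task, matching:** one rule only, "with pleasant and unpleasant stimuli matched for arousal levels".
- **Physiological Measures:** "SC to trauma related cues during the EST and the IAPS procedure will be measured", so skin conductance comes from both the word task and the picture task.

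Aim 1 names the picture task and expects nabilone, propranolol and cannabis each to reduce reactivity to trauma-related material. The subject population section asks for 14 completers from 18 enrolled.

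**The concern.** Matching pleasant to unpleasant images on arousal protects comparisons between image types within a session. The drug question in Aim 1 is a different comparison: reactivity to trauma images in an active session against reactivity in the placebo session. The images in those two sessions are different. If one set of 10 trauma images happens to be milder, that session looks less reactive whatever the drug did.

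A within-subject design is chosen to remove this kind of extraneous variation. Here some of it returns through the stimuli, on an Aim 1 measure, with 14 completers and 10 images per category. The trauma images are the most exposed, because they are selected person by person and the stated matching rule does not name them.

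Set construction and allocation are study conduct. An analysis plan cannot rotate image sets once the sessions have been run.

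**Working it through.** **Counts from the protocol.** Images per session: 4 categories × 10 = 40. Per participant over four sessions: 4 × 40 = 160, of which 4 × 10 = 40 are trauma images. The 14 completers cannot be reproduced, because no effect size, SD, alpha or power is given.

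**Inputs that must be assumed.** Let σ be the SD, within a category, of the reaction that single images evoke. Let d be the SD of the within-person drug-placebo difference without image-set noise. Neither is in the document. I take f = σ/d from 0.25 to 1.5 and a two-sided 5% test.

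**Step 1: one participant.** The mean of 10 images has SD σ/√10 = 0.32σ. The difference between two unmatched sets has SD σ√(2/10) = 0.45σ. For a trauma-minus-neutral score it is σ√(4/10) = 0.63σ.

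**Step 2: precision of a drug-placebo contrast.** The variance is multiplied by 1 + 0.2f², and the standard error by its square root. The power column starts from a contrast with 80% power at n = 14 (standardized paired effect 0.81).

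| f | Variance factor | Rise in standard error | Power |
|---|---|---|---|
| 0.25 | 1.0125 | 0.6% | 79.5% |
| 0.5 | 1.05 | 2.5% | 78.1% |
| 1.0 | 1.20 | 9.5% | 72.5% |
| 1.5 | 1.45 | 20% | 64.4% |

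**Step 3: bias or noise?** A simulation with n = 14 and 40,000 runs gave the contribution of image sets to the mean contrast, in units of σ. Type I error comes from 8,000 paired t-tests per case, at f = 0.5 and f = 1.0.

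| Allocation of sets | Mean | SD | Type I error |
|---|---|---|---|
| Images drawn at random for each participant | 0 | 0.12 | 5.1%, 5.3% |
| One fixed set per session number, drug order random | 0 | 0.12 | 5.0%, 5.0% |
| Fixed sets, Latin square of drug order | 0 | 0.03 | 4.9%, 3.7% |
| Sets tied to drug condition (not stated in the protocol) | 0 | 0.45 | 12%, 29% |

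The first row agrees with the formula: 0.447/√14 = 0.12. In the last row the mean is zero only over repeated choices of sets. In any one trial the set difference is fixed, and more participants do not reduce it.

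In the Latin-square row the test becomes conservative at f = 1.0. Rotation cancels most of the set effect in the mean, but a plain paired test still counts it in the standard error. The gain shows only if the analysis accounts for set. With 16 completers the cancellation is exact. With 14 = 3 × 4 + 2, each pairing of set and condition occurs three or four times.

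**Step 4: what matching can recover.** If image values explain a share r of σ², the variance factor becomes 1 + 0.2f²(1 − r). At f = 1.0, assumed shares of 0.25, 0.5 and 0.75 reduce the 9.5% rise to √1.15 − 1 = 7.2%, √1.10 − 1 = 4.9% and √1.05 − 1 = 2.5%.

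**The case against.** The strongest reply is that the protocol is silent here, not wrong. It does not say the sets are unmatched, and set construction may sit in a task manual. That stands. If the sets are already equated, a sentence saying so answers that part of the point.

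Second, a reader might infer that the drug contrasts are biased or the error rate inflated. The text does not support this. Drug order is randomized and image presentation is described as randomized, so the expected contribution of the sets is zero and type I error stays near 5%. Inflation needs sets tied to drug condition, which the protocol does not state. However, randomized presentation may mean only the order within a session, so the pairing of sets with drugs is left open and should be stated.

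Third, not repeating images is a sensible guard against habituation. I agree, and do not treat it as an error.

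Fourth, the size rests wholly on assumed SDs, and at the low end it is negligible. Matching also cannot remove a person's idiosyncratic reaction to a trauma image. Both points stand and limit the claim.

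Fifth, skin conductance during the Emotional Stroop Task involves no images and is unaffected. Correct; only skin conductance during the picture task is at issue.

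Sixth, 40 well-matched images may not exist for every trauma type, and some participants may have several types. The protocol already needs 40 distinct trauma images per person, so the request is to sort those, within type as far as possible.

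**Conclusion.** The point holds as one of precision and clarity. The protocol fixes different images for each session, states matching only between pleasant and unpleasant images, and does not say how the four sets are equated or paired with drug conditions. Drug-placebo contrasts on picture ratings and on picture-task skin conductance therefore carry image-set noise that could be reduced cheaply.

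The loss ranges from trivial (0.6% on the standard error) to appreciable (20%) over an assumed image SD of 0.25 to 1.5 times the paired-difference SD. Only part of it is recoverable. The documents do not allow a narrower figure, and they do not show bias. The change is worth making because it is inexpensive and the trial has only 14 completers.

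**What to change.** In the Visual Cue Task paragraph of the protocol:

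- Keep the rule that images are not repeated across sessions.
- Sort each category into four sets of 10 with similar valence and arousal values. For trauma images, sort each participant's 40 images in the same way, within trauma type as far as possible.
- Assign sets to drug conditions by a rotation list, so that each set meets each condition about equally often. Exact balance is not possible with 14 completers, and dropout may disturb it further. For trauma images, where sets differ between people, the gain comes mainly from the matching.
- State what is randomized: the order of images within a session, the allocation of images to sessions, or both.
- Include image set, or the image's valence and arousal value, in the analysis of picture-task outcomes, so that the gain shows in the standard error. For trauma images the image value is the more useful term.

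The cost is one-time sorting of images the study already needs, a rotation list and one extra model term. No visit, image or procedure is added.

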Aim 1. Compare the effects of nabilone (0.0 and 4.0 mg), propranolol (0.0 and 40.0 mg; [Schwabe et al., 2012; Hurlmann et al., 2010; Alexander et al., 2007; Grillon et al., 2004; Cahill et al., 1994; Hartley et al., 1983; Currie et al., 1988]), and smoked cannabis (0.0 and 5.6% THC) on subjective processing and emotional and physiological reactivity to trauma-related stimuli using the Emotional Stroop Task (EST; McNally et al., 1990) and to trauma-related images selected from the International Affective Picture System (IAPS; Lang et al., 1997) in non-treatment seeking cannabis smokers with PTSD. We hypothesize that under placebo conditions trauma-related stimuli will increase reactivity in both tasks relative to neutral and positive cues. We expect nabilone, propranolol, and cannabis to decrease this reactivity.

Aim 2. Compare the abuse potential of cannabis, nabilone, and propranolol in cannabis-using individuals with PTSD. Subjective drug effects associated with abuse potential, positive and negative drug effects will be measured throughout the session. Based upon earlier findings (Bedi et al., 2012; [name] et al., 2013) in healthy non-treatment seeking cannabis smokers, nabilone is hypothesized to elicit lower subjective ratings associated with drug-abuse liability and intoxication relative to cannabis, supporting its use in treatment for this population. We do not expect that propranolol will engender positive subjective effects associated with abuse liability.

Exploratory Analysis:

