Procedure: Participants will be instructed not to smoke cigarettes or cannabis after midnight the evening before sessions; compliance will be verified by assessing carbon monoxide exhalation. Tobacco smokers will be allowed to smoke cigarettes at consistent times during each session to prevent nicotine withdrawal (Parrott, 1995). Before each session, alcohol use will be measured using a breathalyzer test and illicit drug use will be measured using urine drug toxicology. If individuals are positive for any drugs other than cannabinoids, the session will be rescheduled. Women will have a urine pregnancy test and blood drawn to measure estradiol and progesterone to assess menstrual cycle phase. A standardized light breakfast will be served and baseline assessments completed. Baseline assessments will include monitoring of resting heart rate, as well as seated and standing blood pressure. If heart rate is less than 55 beats per minute, and/or seated or standing blood pressure is less than 90/60 mmHg, study drugs will not be administered and the session will be rescheduled. During each session, Nabilone (0 mg or 4 mg) and propranolol (0 mg or 40 mg) will be administered followed by cannabis smoking (0.0 or 5.6% THC) according to our cued-smoking procedure (Foltin et al. 1987) (Table 2). To examine attentional bias toward trauma-related stimuli and subjective and emotional processing to a range of trauma-and non-trauma-related images, the Emotional

Stoop Task (EST) and the International Affective Picture System (IAPS; Lang, Bradley, and Cuthbert, 1997) will be used. These procedures will begin 120 minutes after nabilone administration, 60 minutes after propranolol administration, and 10 minutes after cannabis smoking. Cue reactivity using the EST and drug-related subjective effects will be assessed throughout the session in order to assess these effects before, during, and after T_{max} for each drug condition. Drug administration will be randomized, double-blind, and double dummy.

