Subjective Effects Battery: The 21-item self-report State Anxiety Questionnaire (STAI; Spielberger et al., 1971) will be used to assess anxiety. Mood and Drug Effect visual analog scales (MDE-VAS) will include subjective ratings indicative of PTSD symptomatology (e.g., 'I feel anxious,' 'I feel on guard,' 'I feel jumpy,' 'I feel emotionally numb'), abuse liability (e.g., 'I like' the capsules) and drug craving (e.g., 'I want cannabis;' [name] et al., 2004).

Cannabis and Capsule Rating Forms ([name] & [name], 2010) will consist of 5 VAS questions (drug strength, good effect, bad effect, drug liking, and willingness to smoke the cannabis again or take the capsule again). The subjective effects battery will be completed before capsule administration and several time-points after capsule administration and cannabis smoking. [The capsule and cannabis rating forms will only be done after capsule administration and cannabis smoking.]

You can upload charts or diagrams if any

Criteria for Early Discontinuation

Criteria for Early Discontinuation

1) *Symptom Provocation:* Before each session, participants will complete **the PTSD Checklist for DSM-5 (PCL-5; Weathers et al., 2013)**, which will ask participants to rate the **incidence** of PTSD symptoms either in the past week or from the previous session. Significant increases in scores from the previous session will be flagged and a clinician will discuss the severity of symptoms with the volunteer and determine the safety of proceeding with the session and study participation. If symptom provocation suggests increased severity of PTSD from mild or moderate to "severe" the patient will be removed from the protocol. Clinical staff will undertake a risk assessment and determine the appropriate course of action.

2) Participants may be discontinued if they fail to follow the study procedures.

3) Participants may be discontinued if they request treatment during the study.

4) Individual study sessions will be rescheduled and study drugs will not be administered if participants have resting heart rate < 55 beats per minute at baseline or evidence of hypotension or orthostatic hypotension (seated and or standing blood pressure < 90/60 mmHg)

Blood and other Biological Samples

Please create or insert a table describing the proposed collection of blood or other biological specimens

We will do a complete blood chemistry and a plasma pregnancy test (15 ml blood) at screening.

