We will perform urine pregnancy tests before each laboratory session, in addition to doing urine drug tests.

At the beginning of each session, 10 mls of blood will be drawn from all participants. This blood sample will be used to determine plasma hormone levels for female participants. We will draw blood from all participants to control for any potential effects that the blood draw may have on behavior.

Assessment Instruments

Create a table or give a brief description of the instruments that will be used for assessment

PTSD / Trauma assessments during screening:

Trauma Interview - interview that relates to the volunteer's trauma history, current symptoms, and frequency of symptoms - 10 min

Extended self-report Life Events Checklist (Weathers et al., 2013) - 10 min

The Modified Sexual Experiences Survey, MSES; Koss & Gidycz, 1985; Messman-Moore et al., 2000) - 10 min

PTSD Checklist for DSM-5 (PCL-5; Weathers et al., 2013) - 10 min

Mini International Neuropsychiatric Interview (MINI) - 20 min

Assessments during sessions

PCL-5 - 10 min

Emotional Stroop Task (Stroop, 1935; Cassidy et al., 1992; Ashley et al., 2013) - 5 min

Visual-Cue Task (Bradley and Lang, 1994; Lang et al., 1997) - 20 min

State Anxiety Questionnaire (STAI; Spielberger et al., 1971) - 3 min

Mood and Drug Effect Questionnaire ([name] et al., 2004) - 2 min

Capsule Rating Form (CRF; [name] and [name], 2010) - 2 min

Marijuana (Cannabis) Rating Form (MRF; [name] and [name], 2010) - 2 min

Physiological assessments: Skin conductance, heart rate, seated and standing blood pressure

Please attach copies, unless standard instruments are used

Off label and investigational use of drugs/devices

Choose from the following that will be applicable to your study

✓ Drug

Select the number of drugs used in this study

3

Drug #1

Name of the drug

Cannabis

Manufacturer and other information

NIDA supplies cannabis cigarettes

Approval Status

IND is approved

IND#

36,369

Who holds the IND/IND sponsor?

IND is held by PI/CU Investigator

[name], PHD

Drug #2

Name of the drug

Nabilone

Manufacturer and other information

Meda Pharmaceuticals

Generic Name - Nabilone

Other name - Cesamet

Manufacturer - Meda Pharmaceuticals, Somerset, NJ 08873-4120

Approval Status

No IND is required

Choose one of the following options

FDA conditions are met (see 'Rules')

Explain

FDA conditions are met

Drug #3

Name of the drug

Proranolol

Manufacturer and other information

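### Does rating liking separately for capsules and cigarette, in sessions that give both, bias Aim 2 towards a lower score for nabilone?

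*Protocol*

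**What the plan says.** Aim 2, under Specific Aims and Hypotheses in the Protocol, compares the abuse potential of cannabis, nabilone and propranolol: "nabilone is hypothesized to elicit lower subjective ratings associated with drug-abuse liability and intoxication relative to cannabis". It adds that abuse-related effects and positive and negative drug effects are measured throughout the session.

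Under Drugs, and again under Procedure: "Drug administration will be randomized, double-blind, and double dummy". Procedure adds: "During each session, Nabilone (0 mg or 4 mg) and propranolol (0 mg or 40 mg) will be administered followed by cannabis smoking". On the timing of the cue tasks: "These procedures will begin 120 minutes after nabilone administration, 60 minutes after propranolol administration, and 10 minutes after cannabis smoking". The same section says that drug-related subjective effects are followed over the session so as to cover the period around the peak of each drug condition.

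The Subjective Effects Battery describes three kinds of rating:

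- The mood and drug-effect visual analog scales (VAS). Their abuse-liability content is introduced by one example, "abuse liability (e.g., 'I like' the capsules".
- The cannabis and capsule rating forms, each with five VAS questions: strength, good effect, bad effect, "drug liking, and willingness to smoke the cannabis again or take the capsule again".
- The state anxiety questionnaire.

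A bracketed sentence restricts the forms: "The capsule and cannabis rating forms will only be done after capsule administration and cannabis smoking". Assessment Instruments lists both forms among the assessments made during sessions and ties neither to a drug condition.

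**The concern.** In the nabilone session the participant takes active capsules and later smokes an inactive cigarette that looks the same as an active one. There is one drug experience and there are two products to credit it to. Nabilone is described as a synthetic analog of THC, so its effects could plausibly be put down to the cigarette.

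If Aim 2 then set the capsule form (nabilone session) against the cannabis form (cannabis session), any nabilone liking credited to the cigarette would be lost from nabilone's score. The loss would run in the hypothesised direction, and Aim 2 says that a lower score would support nabilone's use in treatment. None of the abuse-liability items that are named is free of a product, and a rating that was never asked cannot be created at analysis. On that reading the study could report that nabilone is liked less than cannabis when the two are liked equally.

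**Working it through.** **Timing.** From the Procedure section, nabilone to the end of smoking is 120 − 10 = 110 minutes. The propranolol (or dummy) capsule to the end of smoking is 60 − 10 = 50 minutes. Leakage in either direction is therefore conceivable.

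**Size of the feared bias.** The protocol gives no figure to reproduce. The only input from it is 14 completers (Description of Subject Population). Assumed: true liking of 50 mm for both drugs, SD of the paired difference 25 mm, two-sided 5% level. Let *a* be the share of nabilone liking credited to the cigarette and *b* the share of cannabis liking credited to the capsules.

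- Capsule form, nabilone session: 50(1 − *a*)
- Cannabis form, cannabis session: 50(1 − *b*)
- Gap = 50(1 − *b*) − 50(1 − *a*) = 50(*a* − *b*)
- Noncentrality = gap / (25/√14) = gap / 6.68, with 13 degrees of freedom

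| *a* | *b* | Gap (mm) | Chance of a false finding that nabilone is lower |
|---|---|---|---|
| 10% | 0 | 5 | 10% |
| 25% | 0 | 12.5 | 41% |
| 50% | 0 | 25 | 93% |
| 25% | 10% | 7.5 | 18% |
| equal shares | equal shares | 0 | 2.5% |

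With *a* = 10% and *b* = 25% the gap is −7.5 mm, and the false finding is that nabilone is higher (18%). At a gap of 12.5 mm, an SD of 20 or 30 mm gives 58% or 30%. So even the sign depends on two shares about which the protocol holds no information.

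**Same model, scored by session.** Add the two forms within each session:

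- Nabilone session: 50(1 − *a*) + 50*a* = 50
- Cannabis session: 50(1 − *b*) + 50*b* = 50
- Gap = 0 for every *a* and *b*

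For example, with *a* = 25% and *b* = 10% the sums are 37.5 + 12.5 = 50 and 45 + 5 = 50. At a gap of 0 the chance of a false finding that nabilone is lower is 2.5%, whatever the SD of the sum. If each form also carries a constant background *c*, both sums become 50 + 2*c* and the difference is still 0. The leaked liking is not lost; it is on the other form.

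**Is that contrast available?** It needs both forms in both sessions. Assessment Instruments limits neither form to a condition, and withholding a form where its product is inactive would sit badly with the blind. It also needs the session to identify the drug. Four sessions and three active drugs imply at most one active product per session, although Table 1 is not shown.

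**Which contrast does the text describe?** Aim 2 compares drugs. Procedure speaks of drug conditions. No sentence sets one form against the other, and a comparison of sessions fits this wording at least as well.

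**Is a source-neutral item missing?** One example is given for the abuse-liability items of a cited scale, and the scale and forms are not shown. Aim 2 also covers intoxication and positive and negative drug effects, so the full set probably holds more than the example. The text does not show that no source-neutral item is collected.

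**Are capsule ratings before smoking ruled out?** The bracketed restriction covers the two forms. The capsule-liking item belongs to the mood and drug-effect scales, which it does not cover. With 110 minutes available and effects followed through the session, that item may be rated before the cigarette. Table 2 would settle this and is not shown.

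**The case for a change.** The strongest case for the concern is this. Each named abuse-liability rating does refer to a product, and no intoxication item is named although Aim 2 predicts lower intoxication. Dry mouth, headache and dizziness appear among the listed side effects of both nabilone and cannabis, so misattribution under the blind is plausible. The bracketed timing sentence can mean each form after its own product, or both forms only after both products; on the second reading no capsule form is free of the cigarette. Some ways of combining the forms do not help: taking the larger of the two gives 45, 37.5 or 25 mm for nabilone against 50 mm for cannabis, so the gaps of 5, 12.5 and 25 mm are unchanged. Which items are asked is a matter for the protocol.

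The factual parts stand. So does the point that an overall-liking item would be a more direct measure than a sum, because liking on two separate scales need not trade off one for one. But the feared bias rests on that same trade-off. Where it holds, the sum removes the bias; where it fails, the 41% and 93% have no basis either. The participants' familiarity with cannabis, noted under the procedures for minimizing risks, also speaks against much misattribution to an inactive cigarette.

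**Conclusion.** The concern does not hold. It needs a form-against-form contrast that the protocol does not state, and the absence of an item from scales that are described only by example. Within the model that produces gaps of 5 to 25 mm, the ratings as listed give a gap of 0 mm when scored by session, so the comparison is not beyond recovery. How the forms are scored may be left to the analysis plan, which is not at hand. This conclusion assumes that both forms are completed in every session and that at most one product is active per session; the text supports both, but Tables 1 and 2 and the forms are not shown. An added overall-liking item would be an optional refinement, and its absence from a short list of examples is not an error in the plan.
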